7.10 Safety Analyses

7.10.1 Adverse Events

AEs and SAEs will be coded to system organ class (SOC) and preferred term (PT) with the latest available MedDRA. Adverse event analyses will include only treatment-emergent AEs (TEAEs). A TEAE is defined as any AE that newly appeared or worsened in severity following initiation of study drug administration. If the onset date of an AE is missing, the AE will be considered treatment-emergent unless there is evidence to conclude that it is not. AE listings will include all AEs.

The incidence of TEAEs will be summarized by system organ class (SOC), preferred term (PT) and severity. For those TEAEs that occur more than once during the study period, the maximum severity will be used in the summary by severity.

Descriptive statistical summaries (frequencies and percentages) will be provided for the followings:

- Overall summary of number of subjects with: any TEAE; any TEAE related to study drug; any SAE; any SAE related to study drug; any TEAE leading to study drug dose increase, dose reduction, dose interruption; any TEAE leading to study drug discontinuation
- Summary of all TEAEs by SOC, PT and severity
- Summary of TEAEs related to study drug by SOC and PT
- Summaries of TEAEs leading to study drug dose increase, dose reduction, and interruptions by SOC and PT
- Summary of TEAEs leading to early study drug discontinuation by SOC and PT
- Summary of SAEs by SOC, PT, and severity
- Summary of SAEs related to study drug by SOC and PT
- Summaries of TEAEs of special interest (e.g. allergic reactions, gastrointestinal events, renal events)

A listing for all AEs will be provided, including verbatim term, PT, SOC, severity, whether serious, relationship to study drug, onset and end date, action taken, and outcome of event will be provided. A listing of SAEs and TEAEs leading to any study drug modification or discontinuation (increase, reduction, interruption or discontinuation) will also be provided. In addition, listings will be provided for events of special interest.

7.10.2 Death

If there are any deaths, a listing of deaths will be provided.

7.10.3 Clinical Laboratory Tests

For central laboratory test summaries by visit, the central laboratory measurements at scheduled visits will be used if available. The visit name from the central laboratory will be used to determine whether a visit is scheduled or unscheduled.

If a laboratory result from a visit is retested and the central laboratory subsequently determines the original result to be valid, the original result for that visit will be used in analysis, and the second (i.e. ‘retested’) value will be ignored. Otherwise, if the central laboratory detects an error through the retesting, the retested value will be used in analysis as the measurement for that visit.

The baseline central laboratory value is defined as the last non-missing central laboratory value collected on or before the date of the first dose of study medication.

All serum chemistry, hematology, serum fluoride, and plasma parathyroid hormone level results and change from baseline will be summarized with descriptive statistics at each scheduled visit.

The incidence of laboratory test results in ranges of interest will be summarized. These summaries will include but are not limited to the following:

- Serum potassium < 3.0, < 3.5, < 3.8, > 5.0, and \geq 5.5 mEq/L
- Serum magnesium < 1.4, < 1.2, and < 1.0 mg/dL
- Serum calcium > 10.2 mg/dL

Laboratory shift tables from baseline to end of dose finding period and baseline to end of treatment will be presented for serum calcium, magnesium and phosphate.

Listings will be provided for all laboratory parameters. Listings will include test results at both scheduled and unscheduled visits.

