4.1 Inclusion Criteria

Subjects must meet ALL the following criteria:

1. Written assent (when applicable) and written informed consent by a legally authorized representative provided prior to participation in the study
2. Age 2 – < 18 years old (subject's age should not exceed that of the age cohort into which s/he is enrolled for at least the entire 14 days of the PD / Dose Finding Phase)
3. Pediatric subjects with CKD and eGFR < 90 mL/min/1.73 m² calculated using the Schwartz formula as described in Section 7.2, including renal transplant subjects, based on local creatinine measurement at Screening
4. Two blood or serum potassium measurements of 5.1 to < 6.5 mEq/L performed on separate days (see Section 6.1)
5. In the opinion of the Investigator, the subject is expected to require treatment for hyperkalemia for at least 6 months
6. If taking any RAASi, beta blockers, fludrocortisone or diuretic medications, must be on a stable dose for at least 28 days prior to Screening
7. Females of child-bearing potential must be non-lactating, must have a negative pregnancy test at Screening, and must have used an effective form of contraception (e.g., abstinence, hormonal, chemical, physical barrier, etc.) for at least 1 month before patiromer administration. Subjects of child-bearing potential must agree to continue using contraception throughout the study and for 1 month after the last dose of patiromer

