6.5 Other Visits

6.5.1 Safety Visit

Safety Visits are mandatory in certain situations. Mandatory Safety Visits are required within 7 days if subject meets any of the following criteria:

- Local potassium is > 6.0 mEq/L. If the patiromer dose is already at the maximum dose (or anticipated highest dose) for the age group, standard of care for hyperkalemia should be applied including RAASi dose decrease
- Any increase in patiromer dose that is initiated and the next scheduled study visit is > 1 week after the dose increase has been initiated
- Discontinuation per the Investigator's discretion

Note: During the 14-Day PD/Dose finding phase when local potassium measurements > 6.0 mEq/L, the Mandatory Safety Visit is not required if a standard study visit takes place within 3 days, however all listed MSV study procedures must be completed (i.e. ECG) at the standard study visit.

Treatment of these subjects with emergency care for hyperkalemia or prohibited standard of care medications (i.e., sodium polystyrene sulfonate or calcium polystyrene sulfonate) may result in the subject being removed from the study; see Section 5.6 for a complete list of prohibited medications. Investigator must contact the medical monitor to determine if the subject should continue in the study.

The following activities will occur during a Mandatory Safety Visit:

- Subject's visit registration in IWRS
- Vital Signs (resting heart rate and sitting BP)
- 12-Lead ECG if the current or most recent local potassium is > 6.0 mEq/L
- Potassium levels (measured locally and by central laboratory)
- Patiromer dose titration (if needed), dispensation, reconciliation, accountability, compliance, and subject retraining (as applicable)
- Assessment of AEs
- Assessment of concomitant medications
- Next visit scheduling

An unscheduled visit may occur at the discretion of the Investigator. At an unscheduled visit during any phase of the study, the following activities will be performed:

- Subject's visit registration in IWRS
- Assessment of AEs
- Assessment of concomitant medications

Other study procedures described in the protocol including the assessment of potassium levels (measured locally and by central laboratory) may be conducted at the discretion of the Investigator depending upon the reason for the visit.

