Upon receipt of each blood sample for potassium analysis, the central laboratory will perform a semi-quantitative test to assess for evidence of hemolysis. Pre-defined criteria have been established for determining whether the test result is indicative of potential hemolysis. These criteria and the criteria for removing serum potassium value from the efficacy analyses on the basis of hemolysis are described in the Laboratory Manual. When a central laboratory sample has been identified as hemolyzed after it has been received and processed by the central laboratory, the blood draw will not be repeated by the site personnel. The statistical analysis plan (SAP) summarizes how the data analyses will account for the missing central laboratory potassium value. If the central laboratory blood sample has been identified as hemolyzed by the site personnel before it has been sent to the central laboratory, a repeat blood draw can be performed if the subject is still at the site.

When a blood sample, which is used by the site for titration and subject management, has hemolyzed (e.g., by visual inspection of the central laboratory serum sample), the site will need to repeat the potassium measurement from a separate blood draw in order to ensure accurate decision-making regarding patiromer titration.

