- ^k Palatability of patiromer will be evaluated in children ≥ 6 years of age when the initial dose is administered at the study site on Day 1 and parental or legal authorized representative response on the subject's (< 6 years of age) acceptance of patiromer will be assessed on Day 14 (see Section 7.6 for further details).
- ^l ECG at the Mandatory Safety Visit required only if the local potassium is >6.0 mEq/L at the current or prior visit (see Section 6.5.1)
- ^m ECG is only required if the local potassium is > 6.0 mEq/L

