5.2 Safety Endpoints

Safety variables will include:

- All treatment-emergent adverse events (TEAEs)
- Reasons for dosing interruption or discontinuation
- Serious adverse events (SAEs)
- Clinical laboratory test results
- Vital signs
- ECG
- Deaths
- Laboratory safety summaries will include:

- Incidence of potassium (1) < 3.0 mEq/L, (2) < 3.5 mEq/L, (3) ≥ 5.1 mEq/L and (4) ≥ 5.5 mEq/L (measured by central laboratory)
- Incidence of serum magnesium (1) < 1.4 mg/dL (< 0.58 mmol/L), (2) < 1.2 mg/dL (< 0.49 mmol/L) and (3) < 1.0 mg/dL (< 0.41 mmol/L) (central laboratory)
- Calcium levels, phosphate levels, and serum fluoride levels will be assessed based on central laboratory analysis of samples collected at each of the scheduled study visits

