5.4 Study Day and Visit Windows

The Study Day for date of first dosing is Day 1. The Study Day for all other study events is defined as follows:

- If a date is prior to the Reference Date, Study Day is defined as [date] - [Reference Date], so the Study Day for the day before date of first dose (typically the first dosing day) is defined as Day -1.
- If a date is on or after the Reference Date, Study Day is defined as [date] - [date of the first dose] +1; hence, the Study Day for the day after first dose is defined as Day 2.

The protocol specified windows for scheduled visits are included in the Schedule of Events (Appendix A and Appendix B).

Unless otherwise specified, analyses by visit will use the visit weeks reported in the database and include results collected at scheduled visits.

Analyses not limited to visits (e.g. incidence of laboratory test values within a given range, and time to event analyses) will include all available values of the variable of interest, irrespective of whether it was collected at a scheduled or unscheduled visit.

For central laboratory data, the visit information from the central laboratory will be used to determine whether a visit is scheduled or unscheduled.

For all analysis variables, unless otherwise specified, baseline is the last non-missing value of the variable on or before the first dose of any study medication.

Modifications to visit schedules may be required due to Coronavirus Disease 2019 (COVID-19). Depending on the scope of changes needed, additional analyses may be undertaken in order to clarify and assess the impact of the modifications to visit schedules. Descriptions of

the additional analyses to be done in relation to COVID-19, if any, will be provided in the SAP prior to database lock.

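### The planned high-potassium counts stop at 5.5 mEq/L, inside the entry range, and cannot separate a child who stayed near entry level from one who rose above 6.0; separately, no hemolysis rule is stated for them

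*SAP*

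**What the plan says.** Two lists define the potassium incidence counts. SAP 7.10.3 gives "Serum potassium < 3.0, < 3.5, < 3.8, > 5.0, and" ≥ 5.5 mEq/L, introduced by "These summaries will include but are not limited to the following". SAP 5.2 gives < 3.0, < 3.5, ≥ 5.1 and ≥ "5.5 mEq/L (measured by central laboratory"). Neither list names a cut-off above 5.5.

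SAP 5.4 says that analyses not tied to visits, with laboratory incidence counts as an example, "will include all available values of the variable of interest, irrespective of whether it was collected at a scheduled or unscheduled visit". It does not say that baseline or screening values are left out.

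The levels to set beside these are in the protocol:

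- Entry (4.1): "Two blood or serum potassium measurements of 5.1 to < 6.5 mEq/L performed on separate days".
- Mandatory Safety Visit (6.5.1), first criterion: "Local potassium is > 6.0 mEq/L".
- ECG during the dose-finding phase (Appendix A footnote): "ECG is only required if the local potassium is > 6.0 mEq/L". Appendix B has the same footnote for the long-term phase.

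On hemolysis, Protocol 7.1.1 warns of spuriously high results. It says that "the criteria for removing serum potassium value from the efficacy analyses on the basis of hemolysis are described in the Laboratory Manual", and that the SAP explains how the analyses deal with a central value lost in this way. The SAP does not mention hemolysis.

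**The concern.** A count of high values is useful for safety if it separates worsening from the condition that brought the child into the study. Here the upper rows sit at the lower edge of the entry range (> 5.0, ≥ 5.1) or inside it (≥ 5.5). A child who enters at 5.9 and improves to 5.6 falls in the same top row as a child who rises to 6.8.

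This matters because Protocol 1.5 bases the lowest starting doses on an adult dose below the efficacy range. Uncontrolled potassium early in treatment is therefore a foreseeable risk. The protocol treats > 6.0 as the level for action, and in Protocol 1.1 the European cohort analysis labels ≥ 6 as severe hyperkalemia. No planned row reports how many children got there.

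Hemolysis raises a second, independent question: whether a result that reflects the blood draw and not the child can add to the high rows.

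**Working it through.** The plan states no figure for these counts. Its one precision figure (73%, SAP 2.3) concerns the proportion in the target range and plays no part here.

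**Step 1. Compare the cut-offs.** The highest counted level is 5.5, the action level is > 6.0, and the entry range ends just below 6.5. The gap is 6.0 − 5.5 = 0.5 mEq/L. If k children are counted at ≥ 5.5, the number above 6.0 can be anything from 0 to k.

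**Step 2. Children above each cut-off before dosing (illustration).** The documents give no pediatric baseline. I take the adult Phase 3 mean 5.58 and SD 0.51 (Protocol 1.2) and assume a normal distribution truncated to 5.1–6.5:

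P(≥ c) = [Φ((6.5 − m)/s) − Φ((c − m)/s)] / [Φ((6.5 − m)/s) − Φ((5.1 − m)/s)]

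| Assumed mean / SD | > 5.0 | ≥ 5.5 | > 6.0 |
|---|---|---|---|
| 5.58 / 0.51 | 100% | 66.6% | 21.4% |
| 5.4 / 0.30 | 100% | 43.9% | 2.7% |
| 5.5 / 0.35 | 100% | 57.1% | 8.5% |
| 5.7 / 0.40 | 100% | 73.4% | 22.4% |

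If baseline values enter the counts, the > 5.0 row is full from the start and the ≥ 5.5 row holds 44–73% of children. The entry range uses local values and the counts use central ones, so the match is approximate.

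**Step 3. On-treatment values (illustration).** Keep SD 0.51 and vary the mean. The lowest mean is the adult baseline plus the adult change, 5.58 − 1.01 = 4.57. The share of values ≥ 5.5 that also exceed 6.0 is:

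- mean 4.57: 0.0025 / 0.034, about 7%
- mean 5.0: 0.0250 / 0.163, about 15%
- mean 5.5: 0.1634 / 0.500, about 33%

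There are 12 scheduled post-baseline samples: Days 3, 7 and 14, eight long-term visits, and Follow-up Visit 1. If they are treated as independent, the chance of at least one value > 5.0 is 1 − Φ((5.0 − m)/0.51)^12, which is 93% at mean 4.57 and above 99% at 4.8 or more. The chance of any value > 6.0 is 3% at mean 4.57 and 26% at mean 5.0. The > 5.0 row is thus close to saturated over a range where the risk of > 6.0 changes about ninefold. Correlation within a child would lower these figures.

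**Step 4. Look for the > 6.0 information elsewhere.** SAP 7.10.3 plans shift tables for calcium, magnesium and phosphate, not for potassium. By-visit summaries include the maximum (SAP 7.1) but use scheduled visits (SAP 5.4). A value that first exceeds 6.0 at a Mandatory Safety Visit or other unscheduled visit would add to the ≥ 5.5 count, but its level would appear only in listings.

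**Step 5. Hemolysis.** With an assumed flag rate h per sample and independence, the chance that a child has at least one flagged sample is 1 − (1 − h)^n. Twelve is the scheduled maximum. Eight remain if Day 3 and Weeks 3, 10 and 22 are omitted as Protocol 3.2.2 and 3.2.3 allow.

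| h (assumed) | n = 8 | n = 12 |
|---|---|---|
| 2% | 15% | 22% |
| 5% | 34% | 46% |
| 10% | 57% | 72% |

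These are shares of children with any flagged sample. They do not estimate false high-potassium events.

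**The case against.** Three stronger readings are tempting, and the documents do not support them.

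*The planned output cannot show a rise above 6.0.* This is true of the named counts only. Central potassium is part of the chemistry panel and is summarized at each scheduled visit with change from baseline and the maximum. Listings cover scheduled and unscheduled values, and the list of ranges is open-ended. The ECG table partly reflects action-level events, because before Week 26 or early termination most post-baseline ECGs are required only above 6.0. A value that needs treatment or ends dosing is also an adverse event (Protocol 8.1). With at most 54 children, a very high scheduled value would be hard to miss.

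*Hemolyzed samples are kept in the safety counts.* A reader might infer this from SAP 5.4 together with a removal rule described for efficacy. But the SAP 5.4 sentence concerns visit type, not sample validity, and Protocol 7.1.1 goes on to treat the affected central value as missing. The Laboratory Manual is not available here. What can be said is that no rule is stated.

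*Hemolysis is why > 6.0 cannot be seen.* It is not. It would inflate high counts, which is a separate matter.

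It is also fair that the chosen cut-offs have a purpose: 5.0 and 3.8 bound the titration target, and 5.5 is part of the Day 3 up-titration rule. That Day 3 rule, however, also requires the value to exceed the latest local screening result (Protocol 5.2.1), and the safety count drops this second condition. Finally, the trigger is local while the counts are central, so a central > 6.0 row alone would not count triggered actions.

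**Conclusion.** The point holds for the counts. Their upper cut-offs lie at or inside the entry range, nothing limits them to post-baseline values, and the action level has no row. They cannot distinguish persistence at, or improvement from, an entry value of 5.5 or more from a rise above 6.0. Permission to add ranges is not a plan to do so.

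The Step 1 comparison needs no assumption. The percentages do: a pediatric baseline resembling adult data or the stated alternatives, normality, independent visits, and hemolysis rates with no source in the documents. They illustrate the problem and do not predict results.

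The lack of a hemolysis rule is a separate and smaller gap: Protocol 7.1.1 refers the reader to the SAP, and the SAP is silent. Neither gap touches an endpoint, the sample size, alpha or a decision rule. This is a cheap improvement to a descriptive safety table.

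**What to change.** In SAP 5.2 and 7.10.3, and in the same terms in both:

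1. Restrict the potassium incidence counts to post-baseline values, and add central > 6.0 and ≥ 6.5 mEq/L.
2. For ≥ 5.5, also show how many children were above their own baseline, or add a shift table from baseline to maximum post-baseline potassium with unscheduled visits included.
3. Count children with a local value > 6.0 in a separate row, because the ECG and safety-visit trigger is local.
4. Present the high-potassium counts with and without hemolysis-flagged central values, using the Laboratory Manual criteria.

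An exact 95% interval would keep an empty row from being over-read. With no child above 6.0, the upper bound 1 − 0.025^(1/n) is 26.5% for n = 12, 9.7% for n = 36 and 6.6% for n = 54.

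The cost is SAP wording and a few rows from data already collected. One drawback is that a true high value in a flagged tube leaves one of the two versions, which is why both should be shown.

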7.10.4 Vital Signs

Vital Signs and changes from baseline, including resting heart rate, diastolic and systolic blood pressure (BP), weight, and height, will be summarized using descriptive statistics at each scheduled visit for vital signs. A listing for vital signs, weight, and height will be provided.

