1.5 Rationale for Patiromer Starting Doses

The starting doses of patiromer in each age cohort were selected based on the median weights for boys and girls within each of the three age categories using standard growth data (CDC, 2010). The initial weight-based doses selected were guided by the starting dose in adults (8.4 g/day patiromer), a higher commonly used dose in adults (16.8 g/day) and a dose below the adult efficacy range (4.2 g/day patiromer) in the event children have a different response profile than adults.

Patiromer dose titrations up and down are allowed to achieve and maintain potassium in the target range of 3.8 – 5.0 mEq/L. The titrated increment or decrement is planned to be the lowest starting dose for each age group.

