5 STUDY TREATMENTS

5.1 Treatment Blinding

The study is open-label and non-randomized.

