6.2.6 Week 26 Visit

The Week 26 Visit is the last visit of the Long-Term Treatment Phase. This visit is performed approximately 6 months after the Baseline Visit (Day 1) and the next day following administration of the last dose of patiromer.

The activities for Week 26 (\pm 7 days) are detailed below and Appendix B:

- Subject's visit registration in IWRS
- Physical examination
- Body weight and height
- Vital Signs (resting heart rate and sitting BP)
- 12-Lead ECG
- Potassium levels (measured locally and by central laboratory)
- Other central laboratory tests (see Appendix C):
 - Serum chemistry
 - Plasma parathyroid hormone
 - Serum fluoride
 - Urinalysis (not required for anuric subjects, see section 7.2)

- Hematology (CBC)
- Urine pregnancy test (female subjects of child-bearing potential only; measured locally and by central laboratory). In the event of a positive or equivocal urine pregnancy test result or if the subject is anuric, a serum Pregnancy test will be performed.
- Patiromer reconciliation, accountability and compliance
- Assessment of AEs
- Assessment of concomitant medications
- Next visit scheduling

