2.2 Study Design

[figure not shown]
Up to 54 subjects, 2 – < 18 years of age with CKD and hyperkalemia will be enrolled in this open-label, multiple-dose, Phase 2 study. Subjects must be < 18 years of age from the time of study consent until anticipated completion of Day 14 of the study.

The study will include two treatment phases: PD / Dose Finding Phase consisting of the initial 14-day dose finding period followed by an up to 5.5-month Long-Term Treatment Phase for a total study participation duration for individual subjects of up to 6.5 months (see Figure 1). The overall design of the study is presented schematically below.

The study periods comprised of the following (Figure 1):

- Screening Period (up to 7 Days)
- PD / Dose Finding Phase (14 Days)
- Long-Term Treatment Phase (5.5 Months)
- Follow-up Period (14 days after discontinuation of treatment, whether subject completes treatment or discontinues early)

Figure 1: Study Schema

D = day; PD = pharmacodynamic; S = screening; W = week.

^a Dosing of patiromer will first be initiated in the oldest age cohort 12 - < 18 years of age followed by 6 - < 12 years of age and subsequently 2 - < 6 years of age. The first starting dose tested in each age cohort will be the lowest starting dose.

^b Dose titration for subjects within a dose group will occur using a protocol specified algorithm (see Section 5.2.1) that is based upon starting dose and targeted to achieve and maintain potassium in the target range (3.8 – 5.0 mEq/L).

^c Subject's eligibility will be assessed during a Screening Period with up to 2 visits (Screening Visit 1, Screening Visit 2). See Section 3.2.1 for details.

^d For subjects who meet all other eligibility criteria, Screening Visit 1 or Screening Visit 2 may be converted to the Day 1 Visit (Baseline). See Section 3.2.1 for details.

^e Follow-up will be 1 and 2 weeks after the last dose of patiromer. Follow-up 1 will be an onsite visit where potassium levels will be measured locally and by central laboratory. Follow-up 2 will be via a phone call unless the investigator requests the subject to return for an onsite visit based on potassium level measured in Follow-up 1.

Note: please see Appendix A and Appendix B for details regarding the study visit window for each scheduled visit including the Follow-up Visits.

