7.3 Demographics and Baseline Characteristics

Demographics and baseline characteristics will be summarized for the ITT and safety population.

The summary of demographic information will include age, gender, race and ethnicity. The summary of patient characteristics at baseline will include, weight, height, and BMI. Baseline medical history will include chronic kidney disease and its etiology, whether patient was on peritoneal dialysis, whether patient ever received a renal transplant, whether patient had diabetes mellitus and its type, , heart failure and its type, ejection fraction percentage, baseline serum potassium and eGFR.

Listings of demographics and baseline characteristics will also be provided.

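### SAP 7.10.4 summarises height and weight only as raw change from baseline, so partial slowing of growth or weight gain would still appear as a positive mean change

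*SAP*

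**What the plan says.** SAP 7.10.4 handles body size within the vital-signs paragraph: "Vital Signs and changes from baseline, including resting heart rate, diastolic and systolic blood pressure (BP), weight, and height, will be summarized", descriptively, at scheduled visits. Individual data follow: "A listing for vital signs, weight, and height will be provided". SAP 5.4 sets the starting point: "baseline is the last non-missing value of the variable on or before the first dose of any study medication". SAP 7.3 adds: "The summary of patient characteristics at baseline will include, weight, height, and BMI". No BMI summary is planned after baseline.

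The setting in which these summaries will be read:

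- **Population.** SAP 2.2: "Up to 54 subjects, 2 – < 18 years of age with CKD and hyperkalemia".
- **Comparator.** None. Protocol 5.1: "The study is open-label and non-randomized".
- **Table layout (SAP 7.1).** Columns by age cohort and starting dose, plus an overall column. Continuous summaries include the median, quartiles, minimum and maximum.
- **Sex.** The sex subgroup in SAP 5.1.3 and 7.9.3 is optional and covers efficacy only.
- **Measurement times (Protocol Appendices A and B).** Height and weight are taken at baseline, Day 14, Weeks 7, 14 and 26, and early termination (ET). Protocol 6.2.5 lets the Week 7 and Week 14 measurements be dropped at a Home Care visit.

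A growth reference appears in one place, Protocol 1.5 (repeated in the synopsis), where the starting doses were "selected based on the median weights for boys and girls within each of the three age categories using standard growth data (CDC, 2010"). Protocol Section 15 has no matching entry. Neither document mentions a z-score, a percentile, a growth velocity, or any comparison with expected growth.

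**The concern.** Most children in this age range gain height and weight over six months whatever the treatment does, and the normal gain depends on age and sex. A raw change is informative only against what was expected. A randomised control arm would supply that expectation, but there is none here, so an external growth reference is the only comparator available.

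The cohort split does not fill the gap. A cohort mixes sexes and spans several years of age. In the oldest cohort it can mix children still growing quickly with adolescents near final height. The overall column averages centimetres and kilograms from toddlers to 17-year-olds.

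At stake is how well the long-term phase can describe growth. This is the first study of the drug in children (Protocol 1.3). The 5.5 months after Day 14 are described as safety follow-up (Protocol 1.4), and safety and tolerability are the secondary objective (Protocol 2). Gastrointestinal events were the most common adverse events in adults (Protocol 1.2), and the severity grades for nausea and vomiting refer to oral intake (Protocol Table 5). Whether weight gain keeps pace is therefore a reasonable descriptive question.

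**Working it through.** **The plan's own figures.** There is no precision or size figure for growth to reproduce. The only computed figure is the 73% lower exact limit for 12 successes out of 12 (SAP 2.3). It reproduces as 0.025^(1/12) = 0.735 and has no bearing on this point.

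**Inputs from the documents.** Follow-up of 26 weeks, about 0.5 year; cohorts of 2 to <6, 6 to <12 and 12 to <18 years, so 4, 6 and 6 years wide; 12 subjects per cohort at the recommended dose (SAP 2.3).

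**Assumptions, none from the documents.** Expected height velocity of 4 to 8 cm/year; reference SD for height of 4 to 8 cm, held constant over the interval; growth halved; a child growing normally keeps the same z-score; expected weight gain of 2 to 5 kg/year.

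**Step 1: height.** Expected gain = velocity × 0.5. Observed gain = half of that. Change in z-score ≈ (observed − expected) / SD.

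| Velocity (cm/year) | Expected gain (cm) | Raw change reported (cm) | z-score change, SD 8 | z-score change, SD 4 |
|---|---|---|---|---|
| 4 | 2.0 | +1.0 | −1.0/8 = −0.125 | −1.0/4 = −0.25 |
| 6 | 3.0 | +1.5 | −1.5/8 = −0.19 | −1.5/4 = −0.38 |
| 8 | 4.0 | +2.0 | −2.0/8 = −0.25 | −2.0/4 = −0.50 |

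The raw change is positive in every row, while the standardised change is negative in every row.

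**Step 2: weight.** Expected gain = 2 to 5 kg/year × 0.5 = 1.0 to 2.5 kg. Halved, it reads as +0.5 to +1.25 kg, again positive.

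**Step 3: why the cohort mean is ambiguous.** Take 12 adolescents and an assumed 6 cm/year for those still growing.

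- All 12 growing at half rate: mean = 12 × 1.5 / 12 = +1.5 cm.
- Six growing normally and six at final height: mean = (6 × 3.0 + 6 × 0) / 12 = +1.5 cm.

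The means agree, although growth is abnormal in one group and normal in the other. The quartiles would differ, but the zeros in the second group could not be told from growth arrest in younger children without each child's age and sex.

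**Step 4: what the planned output would still show.** A child who loses weight, or gains none, appears in the minimum, may move the lower quartile, and can be found in the listing. The gap is therefore partial slowing.

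**The case against.** The strongest case on the other side is that this is a descriptive table and nothing depends on it.

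- No rule, threshold or test treats a positive change as safe. This stands.
- The safety variables in Protocol 9.5 and SAP 5.2 do not name growth, height or weight. Amendment 1 added height to the long-term visits for data completeness, and height is also an input to the eGFR formula in Protocol 7.2. This stands: growth monitoring is not a declared aim.
- New clinically significant examination findings must be reported as adverse events (Protocol 7.4), and the safety committee reviews data throughout the long-term phase (Protocol 8.6.3). This stands, and it limits the gap to slowing that escapes clinical notice.
- Height, weight and demographics are all listed, so z-scores could be derived later. This is true, but a measure chosen after the data are seen, against a reference also chosen then, is weaker than one named beforehand.
- Without a control arm, and with CKD patients including renal transplant recipients, a z-score change cannot separate drug from disease. This stands and should be stated in the SAP. It does not rescue the raw change, which has the same weakness and lacks a reference as well.

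A reader might infer that the plan judges growth safety by raw change, that monitoring growth is the stated purpose of the long phase, or that the data could not reveal any growth problem. The documents support none of these. They set no decision rule, they describe the phase as safety follow-up in general, and the planned output would expose weight loss or absent gain.

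**Conclusion.** The point holds in a limited form. As planned, the height and weight tables cannot tell partially slowed growth or weight gain from normal growth over 26 weeks, and the overall column of raw change has no clear interpretation. This follows from the absence of any standardised measure in either document, the lack of a control arm, and the wide mixed-sex cohorts. It does not depend on the illustrative numbers.

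The size does depend on them. Halved growth would be about −0.1 to −0.5 height z-score units, reported as +1 to +2 cm, under the assumed velocities and SDs. The documents give no growth rates and raise no growth signal for this drug, so the range shows only what could be missed and is not a prediction.

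The consequence is modest. The primary and secondary efficacy analyses are untouched. The change is worth making because it is cheap and makes measurements already being taken interpretable.

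**What to change.** 1. **SAP 7.10.4.** Keep the raw summaries. Beside them add age- and sex-specific z-scores for height, weight and BMI and their change from baseline. Make Week 26 (or ET) the main time point, with Weeks 7 and 14 where measured. Show time since baseline for ET values, because that interval is shorter.
2. **SAP 7.3.** Add baseline z-scores for the same three measures.
3. **Growth reference.** Name the reference and its version in full. The protocol's CDC, 2010 citation will not serve as it stands: it supports median weights only, and the reference list does not contain it. With up to 38 sites globally, the choice should be made deliberately.
4. **Interpretation.** State that, without a control arm and in a CKD population, the z-score change describes growth against the reference and does not attribute it to the drug.

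The cost is a few derived variables, one table, and the decision on a reference. No new measurements are needed. The one thing to confirm is that the database holds age precisely enough to compute it at each visit; inclusion criterion 2 already requires sites to know it well enough to check the cohort limit through Day 14. No protocol amendment is needed, since Protocol Section 9 and SAP Section 1 give the SAP precedence on analysis.
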